3.1 Primary Objectives

The primary objectives for Part 1 (dose escalation) and Part 2 (expansion) of the study are:

- Evaluate the safety and tolerability and determine the maximum tolerated dose (MTD) of ADCT-301 in patients with relapsed/refractory lymphoma (Part 1).
- Determine the recommended dose of ADCT-301 for Part 2.
- Evaluate the safety and tolerability of ADCT-301 in Part 2 at the dose level recommended in Part 1.

3.2 Secondary Objectives

The secondary objectives for Part 1 and Part 2 of the study are:

- Evaluate the activity of ADCT-301 measured by overall response rate, duration of response, progression-free survival, and overall survival.
- Characterize the pharmacokinetic (PK) profile of HuMax-TAC (total antibody; drug-to-antibody ratio [DAR] ≥ 0), PBD-conjugated HuMax-TAC (DAR ≥ 1), and free warhead SG3199.
- Evaluate anti-drug antibodies (ADAs) in blood before, during, and after treatment with ADCT-301.

[REDACTED]

[REDACTED]

[REDACTED]

[REDACTED]

[REDACTED]

[REDACTED]

4 Investigational Plan and Patient Selection

4.1 Study Design

This is a Phase 1, FIH, open-label, dose-escalation (Part 1) and expansion (Part 2) study of ADCT-301 in patients with relapsed and refractory lymphoma. The study will evaluate the safety and tolerability of ADCT-301 as monotherapy, as well as the preliminary activity, PK, pharmacodynamics, and formation of ADAs of ADCT-301 in patients.

For each patient, the study will include a screening period (up to 28 days), a treatment period (until progressive disease, intolerable toxicity, or withdrawal of consent), and a follow-up period to assess disease progression and survival for up to 12 months after the last dose of study drug. The total study duration will be dependent on overall patient tolerability to the study drug and response to treatment. It is anticipated that the entire study (Parts 1 and 2) could last approximately 3 years from first patient treated to last patient completed.

In Part 1, patients will receive ADCT-301 administered as a 1-hour IV infusion on Day 1 of each 3-week (21-day) cycle. If ADCT-301 is well tolerated after the first cycle, the infusion duration may be shortened to 30 minutes for subsequent cycles at the Investigator's discretion.

The first patient at each dose level will be monitored for any AEs for 7 days before proceeding with dosing for the second patient.

The initial dose level for Part 1 will be 3 µg/kg (Dose Level 1). The highest allowed dose will be 300 µg/kg. The MTD will be the highest safe dose that has at least a 60% probability that the dose-limiting toxicity (DLT) rate is < 30%.

After discontinuation of treatment, patients without documented objective disease progression will be followed until progression of disease or initiation of new anticancer therapy for up to 12 months. All patients will be followed for survival (by telephone contact or retrospective chart review) until a new anticancer therapy is initiated or for up to 12 months after treatment discontinuation.

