| Estimated Duration of Patient Participation and Study Duration: | 
For each patient, the study will include a screening period (up to 28 days), a treatment period (until withdrawal, see below), and a follow-up period to assess disease progression and survival for up to 12 months after the last dose of study drug. The total study duration will be dependent on overall patient tolerability to the study drug and response to treatment. It is anticipated that the entire study (Parts 1 and 2) could last approximately 3 years from first patient treated to last patient completed.
 
A patient may be withdrawn from the treatment for any of the following reasons:
 
• Objective disease progression• Clinical progression• AE• Withdrawal of consent• Major protocol deviation• Required treatment delay > 21 days (except in case of potential patient benefit, which must be approved by the Sponsor)• Non-compliance, including lost to follow-up• Pregnancy• Other (e.g., development of contraindications with use of the study drug)• The Investigator determines if it is in the best interest of the patient to discontinue the patient's participation in the study.• Discontinuation of the study by the Sponsor.• Death |

| | |
|--|--|
| Efficacy Assessments: | 
Response to ADCT-301 will be assessed through the evaluation of complete response (CR), partial response (PR), progressive disease (PD), and stable disease (SD) determined by the Investigator based on the Lugano Classification Criteria (2014) and Global Response Score Grading Scales for CTCL. Disease assessments will occur every other cycle for the first 2 evaluations (6 and 12 weeks), and every third cycle (every 9 weeks) thereafter until progression or more frequently, if clinically indicated.
 
Patients who discontinue treatment for any reason other than objective disease progression will continue to be followed with scans approximately every 12 weeks from the last tumor assessment until disease progression, or initiation of a new anticancer treatment. If a patient discontinues treatment for a hematopoietic stem cell transplant, the frequency of imaging will be as per the transplant center standard of care. After documentation of disease progression or start of a new anticancer treatment, patients will be contacted by telephone approximately every 12 weeks for up to 12 months after the last dose of study drug to collect survival information.
 |

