5.1.6 Long-term Follow-up

Patients who discontinue treatment for any reason other than objective disease progression will continue to be followed with scans approximately every 12 weeks from the last tumor assessment until disease progression, or initiation of new anticancer treatment. If a patient discontinues treatment for a hematopoietic stem cell transplant, the frequency of imaging will be as per the transplant center standard of care.

After documentation of disease progression or start of new anticancer treatment, patients will be contacted by telephone approximately every 12 weeks for up to 12 months after the last dose of study drug to collect survival information.

Blood Sample Collection and Adverse Event Monitoring During Long-Term Follow-up

For all patients, PK and ADA blood sample collection will be performed 12 weeks (\pm 1 week) following the last dose of ADCT-301, unless a new anticancer treatment has been initiated.

Patients who test positive for ADAs may be requested to supply additional ADA samples.

For all patients, collection of AEs and SAEs will continue for 12 weeks after the last dose of study drug or initiation of new anticancer treatment (see [Section 7.3.2.2](#)).

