6.4 Dose Delays and Modifications

The Investigator may suspend ADCT-301 dosing for up to 21 days for any patient who experiences a protocol-defined DLT during any treatment cycle.

At the discretion of the Investigator, the dose may also be delayed for up to 21 days for any other toxicity of any grade.

Resumption of dosing with ADCT-301 after any suspension, even when longer than 21 days, is at the discretion of the Investigator, in consultation with the Sponsor, based on assessment of the patient's clinical condition and whether or not the patient is deriving potential clinical benefit from treatment with ADCT-301. Following recovery to Grade 1 or baseline, treatment may resume at the Investigator's discretion.

Patients who resume treatment following a dose delay may, at the discretion of the Investigator, have their dose reduced by 1 dose level in either part of the study. If toxicity reoccurs at a severity that would mandate a dose delay, then the dose may be further reduced 1 dose level. If toxicity reoccurs at such level, then the patient is to be discontinued from treatment. Dose re-escalation is allowed at the investigator's discretion, at maximum to the dose level the patient was initially assigned to.

Patients experiencing certain types of infection during the course of participation in this clinical study also must delay further dosing, as stipulated in [Section 7.3.4.5](#).

Patients experiencing any autoimmune toxicities (e.g. endocrinopathies) \geq Grade 1 need to be followed at least weekly to quickly detect deterioration and modify dosing as per DLT criteria (can be done by telephone unless symptoms worsen).

Patients experiencing the following significant toxicities will be immediately and permanently withdrawn from treatment with ADCT-301:

- Any patient who experiences a Grade 3 or higher hypersensitivity reaction, regardless of premedication, during any cycle of treatment per CTCAE definitions ([Appendix 13.4](#)).
- Any patient who experiences a recurrent Grade 3 or 4 toxicity excluding hematological toxicity.
- Any patient who requires a dosing delay $>$ 21 consecutive days from the planned Day 1 dosing at any time during treatment (except in case of potential patient benefit, which must be approved by the Sponsor).

Neurological toxicities: dose delay/permanent discontinuation

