6.10.3 Diagnostic, Work-up, and Management of Polyradiculopathy/Guillain-Barré Syndrome

It is recommended starting management of polyradiculopathy/GBS with either intravenous immunoglobulin (IVIg) 0.4 g/kg/day for 5 days or plasma exchange (PLEX) once the diagnosis of polyradiculopathy/GBS has been considered by a neurologist; this would be at CTCAE Grade 2 symptoms for neuropathy or Score 1 as per GBS disability scale ([Appendix 13.7](#)).

Diagnostic workup should include:

- Neurology consultation
- MRI spine with and without contrast to rule out compressive lesion and evaluate for nerve root enhancement or thickening
- Electrodiagnostic studies (nerve conduction studies)
- Pulmonary function tests
- Lumbar puncture: CSF typically has albuminocytologic dissociation with protein elevation disproportionate to WBC—although note that CSF WBC are often elevated in GBS associated with immune checkpoint inhibitors
- Serum antibody testing for GBS (ganglioside antibodies) when possible

Management includes:

- IVIg or PLEX as above
- If IVIg and/or PLEX do not result in improvement, consider using steroids¹⁴
- Admission to inpatient unit with capability for rapid transfer to ICU-level monitoring
- Frequent focused neurological examination (at least twice daily)
- Frequent pulmonary function monitoring
- Monitoring for autonomic dysfunction
- Non-opioid management of neuropathic pain
- Treatment of constipation/ileus
- Anticoagulation
- Physical therapy

7 Study Assessments and Procedures

Patients will undergo the procedures at the time points specified in schedule of events ([Appendix 13.1](#)).

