- 22 Patients to receive ADCT-301 intravenously over 1 hours (\pm 15 minutes). If ADCT-301 is well tolerated after the first cycle, the infusion duration may be shortened to a 30-minute intravenous infusion for subsequent cycles at the Investigator's discretion. The IP administration window is \pm 15 minutes.
- 23 Dexamethasone prophylaxis (4 mg BID on Day -1, Day 1, and Day 2) should be administered, unless contraindicated. If Grade 2 or higher infusion-related hypersensitivity reactions are observed in a patient at any time during the study, this patient must receive prophylactic treatment with all subsequent dosing to reduce the risk of hypersensitivity reaction. Prophylaxis for hypersensitivity will supersede stipulations on dexamethasone prophylaxis
- 24 For all patients, collection of AEs and SAEs will continue for 12 weeks (84 days) after the last dose of study drug or initiation of new anticancer treatment. Any SAEs that occur more than 84 days after the last dose of study drug do not need to be reported unless the Investigator considers the event to be related to study drug.
- 25 To include prescription or over-the-counter medication, herbal or naturopathic products within the 14 days prior to Day 1, throughout the study, and for 30 days after last dose of study drug.
- 26 After documentation of disease progression or start of new anti-cancer treatment, patients will be contacted by telephone approximately every 12 weeks for up to 12 months after the last dose of study drug to collect survival information.
- 27 Information on anti-cancer treatment initiated after discontinuation of ADCT-301 to be recorded in the eCRF.

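### Section 4.1 and the synopsis design row end survival follow-up at new anticancer therapy; Section 5.1.6, the synopsis efficacy row and the schedule start survival calls at that same event

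*Protocol*

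**What the plan says.** Two places share one rule. The last paragraph of protocol Section 4.1 and the synopsis Study Design row follow all patients for "survival (by telephone contact or retrospective chart review) until a new anticancer therapy is initiated or for up to 12 months after treatment discontinuation".

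Three places carry another rule:

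- Synopsis, Efficacy Assessments row: "After documentation of disease progression or start of a new anticancer treatment, patients will be contacted by telephone approximately every 12 weeks".
- Section 5.1.6, Long-term Follow-up: "After documentation of disease progression or start of new anticancer treatment, patients will be contacted by telephone approximately every 12 weeks".
- Section 13.1.1, footnote 26: "After documentation of disease progression or start of new anti-cancer treatment, patients will be contacted by telephone approximately every 12 weeks".

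All three continue the calls for up to 12 months from the last dose and give their purpose as collecting survival status. Footnote 27 adds "Information on anti-cancer treatment initiated after discontinuation of ADCT-301 to be recorded in the eCRF".

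The second paragraph of Section 4.1 describes "a follow-up period to assess disease progression and survival for up to 12 months after the last dose of study drug", and the synopsis duration row does the same. Neither mentions a stop at new therapy. Section 5.2 ends a patient's participation when follow-up is complete or consent is withdrawn.

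On analysis, protocol Section 8.6.1.3 and SAP Section 4.9.5 count death from any cause and censor survivors at the last date known alive or last contact.

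**The concern.** Overall survival is a secondary objective in both parts of the study, and it needs deaths to be ascertained after patients move to other treatment. Under the Section 4.1 sentence, a site may stop collecting vital status on the day new therapy starts. Under Section 5.1.6, that day is when the survival calls begin, if progression has not already begun them.

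If some sites followed the first rule, their patients would be censored for overall survival at or near the start of new therapy. The SAP does not plan that censoring. Patients who start another therapy may differ in prognosis from those who do not, so the censoring could be informative. The SAP Section 4.8.2.2 summary of all deaths during the study could also be incomplete for those patients.

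The conflict concerns only patients who start new therapy. Under either rule, a patient who progresses and receives nothing further remains in survival follow-up.

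**Working it through.** The plan gives no figure to reproduce. The check compares the texts, with simple arithmetic on follow-up time.

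**1. Effect of starting new therapy on survival follow-up**

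| Place | Effect | 12 months counted from |
|---|---|---|
| Synopsis, Study Design row | ends it | treatment discontinuation |
| Section 4.1, last paragraph | ends it | treatment discontinuation |
| Synopsis, Efficacy Assessments row | triggers calls | last dose |
| Section 5.1.6 | triggers calls | last dose |
| Schedule footnote 26 | triggers calls | last dose |
| Section 4.1, second paragraph | none stated | last dose |
| Synopsis, duration row | none stated | last dose |

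**2. Can the Section 4.1 sentence be read so that it agrees?** It does not say whether the earlier or the later limit applies. The 12-month limit is worded as a maximum, so the new-therapy clause can act only by ending follow-up sooner. If the later limit applied, follow-up could run past 12 months, against every other statement of the limit. The sentence just before it also uses new therapy as a stop, there for progression follow-up.

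**3. Which rule does the analysis need?**

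- SAP Sections 4.9.4 and 4.9.2 exclude events after subsequent therapy from progression-free survival and duration of response. SAP Section 4.9.5 has no such rule for overall survival.
- SAP Section 4.9.5 accepts start and end dates of later systemic anticancer therapy as evidence that the patient was alive.
- SAP Section 4.8.2.2 leaves deaths after subsequent therapy out of its 30-day count but not out of its count of deaths during the study.

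The SAP thus separates the two situations and expects survival data after new therapy.

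**4. Follow-up at stake.** Take 12 months as 52 weeks from the last dose, and let new therapy start w weeks after that dose. The documents give no w, so the values below are assumed. Maximum survival contact lost = 52 - w weeks.

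- w = 4: 52 - 4 = 48 weeks
- w = 12: 52 - 12 = 40 weeks
- w = 26: 52 - 26 = 26 weeks

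These are upper limits, for a patient who stays alive and in contact to 12 months.

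**5. The two clocks.** Treatment discontinuation is not defined. If it is dated at the last dose, the gap between the clocks is 0. If it is dated at the end of the 21-day cycle, the gap is 21 days (3 weeks). Section 6.4 says that "the dose may also be delayed for up to 21 days for any other toxicity of any grade", so a decision to stop at the end of such a delay gives 21 + 21 = 42 days (6 weeks). A sponsor-approved longer delay would widen the gap.

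**The case against.** The best reply is that the operational text already settles the matter. Section 7 opens with "Patients will undergo the procedures at the time points specified in schedule of events", and the schedule carries the fuller rule. Section 5.1.6, the efficacy row, the second paragraph of Section 4.1 and Section 5.2 all agree with it or are compatible with it. The outlier is one overview sentence, printed twice. This stands as a limit on likelihood: follow-up is lost only where a site acts on that sentence. It does not remove the conflict, since both rules are current protocol text and no order of precedence is stated between them.

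A second reply is that a site that stopped calling would not necessarily lose all later information. Footnote 27 still collects new-treatment information, and SAP Section 4.9.5 takes last-alive dates from later therapy, scans and any other database date. This stands too. It is why 52 - w is a maximum and not an expected loss.

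A reader might go further and infer that overall survival is biased by some number of percentage points, or in a known direction. The documents do not support that. They give no rate or timing of subsequent therapy, no survival after progression, and no sign of how many sites would follow the outlier. Any simulated range would rest wholly on invented inputs. A reader might also infer that the SAP's censoring rules are wrong, but they are consistent with continued follow-up.

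The difference between the clocks is minor, and it vanishes if discontinuation is dated at the last dose.

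**Conclusion.** The wording conflict is real and can be stated with high confidence. Starting new anticancer therapy ends survival follow-up in two places and triggers survival calls in three, and the 12-month limit runs from two different starting points. The rest of the plan fits continued follow-up to 12 months after the last dose.

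The consequence is conditional and modest. At a site that obeyed the outlier sentence, at most 52 - w weeks of survival contact would be lost per patient who starts new therapy, and some later vital status might still be recovered. Possible informative censoring follows from that, but its size and direction cannot be determined. Overall survival is secondary and descriptive. The SAP plans no hypothesis test, and neither the sample size nor the maximum tolerated dose depends on overall survival. The correction is worth making because it is cheap and because missed deaths may be hard to recover later.

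**What to change.** Make the same two edits in the last paragraph of Section 4.1 and in the synopsis Study Design row.

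1. Rewrite the survival sentence so that vital status is collected on every patient, by telephone or chart review, whether or not the patient has progressed or begun other anticancer therapy, until 12 months after the last dose of study drug. This removes the new-therapy stop and the undefined starting point.
2. In the preceding sentence, on progression follow-up, count the 12-month limit from the last dose as well. Otherwise the paragraph would run two clocks. The stop at new therapy in that sentence can remain, since Section 5.1.6 also ends scans there.

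The cost is two sentences in two places. The survival calls are already scheduled in Section 5.1.6 and footnote 26, and patients with neither progression nor new therapy are already followed with scans, so no procedure is added. The SAP needs no edit on this point.

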4.1.1 Dose Escalation and Determination of the Maximum Tolerated Dose (Part 1)

Dose escalation will be conducted according to a continual reassessment method (CRM) ([Section 13.5](#)). Dose levels from 3 to 300 µg/kg are possible.

However, the final number of doses will be dependent on the emergent toxicity profile and will be decided by a Dose Escalation Steering Committee (DESC) ([Section 7.3.1.2](#)). Pharmacokinetic and pharmacodynamic evaluations may also inform decision making.

The DLT observation period for dose escalation will be 1 cycle; however, the adaptive dose-escalation algorithm will incorporate cumulative DLTs occurring through Cycle 3. No intra-patient dose escalation will be allowed during the study. However, once the recommended Part 2 dose(s) is determined, patients receiving lower or higher dose levels of ADCT-301 in Part 1 may be offered continued treatment at the recommended dose.

During Part 1, the DESC may expand enrollment at doses below the current dose level being evaluated as part of the dose escalation process. Additional patients may only be added at a lower dose level provided there is at least 1 patient with documented stable disease. Not more than 10 patients in total can be treated at any dose level unless at least 3 of the 10 patients have documented partial response or better using the 2014 Lugano Classification criteria² or other appropriate measures of response ([Appendix 13.3](#)).

4.1.2 Dose Expansion (Part 2)

In Part 2 (expansion), patients will be assigned to receive the recommended dose(s) of ADCT-301, as determined by the DESC during Part 1 of the study.

The following dosing regimen(s) may be investigated based on safety and PK emerging information:

- 45 µg/kg every 3 weeks for 3 cycles followed by 30 µg/kg every 3 weeks for patients who have not progressed.
- 45 µg/kg every 3 weeks for 3 cycles followed by 20 µg/kg every 3 weeks for patients who have not progressed.
- 45 µg/kg every 3 weeks for 4 cycles followed by 30 µg/kg every 3 weeks for patients who have not progressed.
- 45 µg/kg every 3 weeks for 4 cycles followed by 20 µg/kg every 3 weeks for patients who have not progressed.

The patient population (e.g., disease subtypes) to be enrolled in Part 2 (expansion) may be refined based on results and observations from Part 1.

4.2 Selection of Study Population

It is estimated that approximately 140 patients (approximately 80 patients in Part 1 and approximately 60 patients in Part 2) will be enrolled at approximately 10 sites in Part 1 and 13 sites in Part 2 of the study. Patients will be assigned to a study treatment only if they meet all of the inclusion criteria and none of the exclusion criteria.

